**Social support** and isolation will be measured with the Adolescent Trials Network (ATN) iTech short measure of the Patient-Reported Outcomes Measure Information System (PROMIS) Social Relationship scales.

**Psychological distress** is operationalized as depression, anxiety and posttraumatic stress. Measurement of these variables is described below.

**Depression** will be measured with the Patient Health Questionnaire (PHQ-9). The PHQ-9 includes 9 items from the DSM-IV criteria for depression with scores on a 4-point Likert scale (0=not at all, 3=nearly every day). Depression is scored as mild, moderate, moderately severe, and severe using composite scores of 5, 10, 15, and 20, respectively. Higher scores are associated with decreased functional status as measured by the SF-20 and scores  $\geq 10$  have a sensitivity and specificity of 88% for major depression. The measure has been used among HIV+ AYA in the United States with a Cronbach's  $\alpha$  of 0.89.

**Question 9 on the PHQ-9 reads:** “Over the past 2 weeks, how often have you been bothered by any of the following problems?..Thoughts that you would be better off dead or of hurting yourself.” If a participant responds “several days”, “more than half the days” or “nearly every day” to this PHQ-9 question at any of the scheduled visits (baseline, 12 or 24-weeks), the project manager will contact the lead PI ([name]) and contact PI at NYU([name]) for guidance.

More specifically, if the participant is at imminent risk for suicide, law enforcement will be notified by Drs. [name] or [name], who will call 911. [name] ( contact PI and licensed clinical psychologist) and [name] (board certified/licensed pediatric nurse practitioner) will also Zoom into the videoconferencing session for crisis management. Full details of managing adverse events are described on pages 15-20 in the Data and Safety Monitoring Plan.

**Generalized anxiety disorder (GAD)** will be measured with the Generalized Anxiety Disorder - 7 (GAD-7). The measure has demonstrated validity and includes 7 items about symptoms in the past two weeks. Scores  $\geq 10$  indicate a probable case of GAD, with scores  $\geq 15$  considered to be severe. Higher scores on the GAD-7 are associated with decreased functional status as

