**For participants who have reached the age of majority, that is, who are ages 18 years and older,** confidentiality will not be maintained: (1) in the event the participant has perpetrated sexual abuse on a minor; (2) in the event the participant has perpetrated physical abuse on a minor; (3) if a participant reports current suicidality and is in imminent danger of suicide; and (4) if a participant reports current homicidality or a serious threat of physical harm to others. There are no other circumstances when confidentiality will be violated.

The following actions will be taken if any of these four circumstances is identified:

**Child sexual or physical abuse.** Child abuse will be reported to the local child protective services agency by [name] who is a mandated reporter and complies with New York State Child abuse laws.

**Suicidality.** If participants are at imminent risk for suicide, law enforcement will be notified by Drs. [name] or [name] who will call 911. [name] (contact PI at NYU and licensed clinical psychologist) and [name] (board certified/licensed pediatric nurse practitioner) will Zoom into the videoconferencing session for crisis management.

**Homicidality or a serious threat of physical harm to others.** When participants are at imminent risk for committing homicidal acts, law enforcement will be notified by Drs. [name] or [name] who will call 911. [name] (contact PI at NYU and licensed clinical psychologist) and [name] (board certified/licensed pediatric nurse practitioner) will Zoom into the videoconferencing session for crisis management.

As part of the informed consent process, participants will also be informed that all information they provide in interviews and intervention sessions is confidential with these exceptions. The NYU IRB recommends the following language be used in the Confidentiality section of the consent form:

*“However, if you are in imminent danger of committing suicide or homicide the appropriate agency or authority will be contacted; and, if you are under 18 and currently being sexually or physically abused, or, if 18 or older, physically or sexually abusing someone else, a report will be made to the local child protective services organization or appropriate authority or organization.”*

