All computerized data, including REDCap, (survey measures, viral load, etc.) will be collected using computers that are double password-protected and are only labeled with participant identification numbers. All study data collected in REDCap will be exported to EXCEL on a every three months and transferred to the NYU Meyers secure server for back-up, which is also double password protected and available only to the research team. Peer health coaches will not be entering, cleaning, and/or analyzing data with the primary role of delivering the intervention. Peer health coaches will therefore not require and/or have access to the NYU Meyers shared drive or the REDCap platform. Peer health coaches will be meeting remotely with study participants via HIPAA compliant Zoom videoconferencing as part of the intervention and regularly attend study team meetings.

A master database that contains participant identifying information and participant identification (PID) numbers will be stored on REDCap. This data will be downloaded monthly into a project-specific folder on the NYU Meyers secure server. This folder is double password protected and can only be accessed by the study's staff members. NYU Meyers staff members who are not members of the research team for this study do not have access to this folder.

**Adverse Events.** Federal regulation (21 CFR Part 312) defines an "adverse event" (AE) as any untoward occurrence involving a study participant, or individual connected to the participant, occurring during the course of the study (including the study's follow-up period). Adverse events are categorized as either a Serious Adverse Event (SAE) or an Adverse Event (AE). **Adverse events are defined as negative experiences that do not involve imminent danger. Serious adverse events are negative experiences that involve imminent danger.**

**Adverse events or serious adverse events are not expected during the course of this study.** However, during the ACCESS-II study sessions 4 through 6, peer health coaches will explore participant's history and experiences with HIV stigma and disclosure concerns and related psychological distress and substance use. There is a potential for a participant to experience discomfort, depressive symptoms, anxiety and/or anger during this session and/or any of the ACCESS II RCT sessions. Peers health coaches will receive adequate training and supervision to minimize this potential.

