**Reporting Adverse Events. This study is no more than minimal risk and adverse events are not expected.** In the event of an adverse event during the intervention - remote videoconferencing sessions (i.e. discomfort, depressive symptoms, anxiety and/or anger), the peer health coach will verbally (phone or in person) notify the project manager, [name] and [name] immediately. If the participant is from Jacobi Medical Center, [name] (clinician co-investigator at Jacobi) will be notified immediately to discuss whether or not mental health referral is needed. If the participant is recruited from North Central Bronx, [name] may collaborate with [name] (physician collaborator) to discuss whether or not mental health referral is needed. If the participant is from BronxCare Health System, [name] (physician collaborator at BronxCare Health System) will be contacted, if deemed necessary. If a participant is recruited from other methods of recruitment, the physician of that participant will be contacted, if deemed necessary. For participants recruited from other recruitment sites, [name] with co-investigators will discuss if mental health referral is needed. All participants will be recruited from clinical sites staffed with psychosocial professionals (psychologists, social workers, and one psychiatrist) who would be available if referral to mental health services is needed.

In the event of a serious adverse event such as suicidal or homicidal ideation, the institutional emergency protocol of the clinical sites (Jacobi Medical Center (North Central Bronx Network, and BronxCare Health System), will be followed. This includes immediate referral to 24-hour psychiatric emergency services via the psychiatric emergency room. This protocol also includes referral to a 24-hour crisis number, [name] with counselors available at all times. Additionally, the clinical site would be contacted immediately to notify clinical staff and if the SAE occurs after hours, an on-call physician may be reached 24 hours a day. In the event of an imminent life threatening emergency, 911 would be notified.

As noted in our consent form, we are obligated to break confidentiality of participants in the event of sexual and physical abuse, or if they report current suicidality or homicidality. If participants are at imminent risk for suicide during in-person interview (focus group or post intervention interview), they will be escorted to a hospital emergency room where appropriate,

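### The plan sets two incompatible thresholds for suicidality, one requiring imminent danger and one not, both for what is a serious adverse event and for when confidentiality is broken

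*Combined protocol and SAP*

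**What the plan says.** Five parts of the combined protocol and SAP bear on this.

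- **Adverse Events (under Data Monitoring).** The only dividing line between the two classes is imminent danger: "Serious adverse events are negative experiences that involve imminent danger", and events without it are plain adverse events. The same section, describing peer-coach training, lists suicidal and homicidal ideation among serious adverse events with no such condition.
- **Reporting Adverse Events.** "In the event of a serious adverse event such as suicidal or homicidal ideation, the institutional emergency protocol of the clinical sites" is to be followed, and this includes immediate psychiatric emergency referral. A call to 911 for an imminent life-threatening emergency is listed separately. On confidentiality, citing the consent form, the team is "obligated to break confidentiality of participants in the event of sexual and physical abuse, or if they report current suicidality or homicidality". Later text has the Vice Dean and the IRB Chairperson decide together whether a reported event is serious.
- **Exceptions to Confidentiality (Data and Safety Monitoring Plan).** The suicide-related exception applies "if a participant reports current suicidality and is in imminent danger of suicide". The section says nothing outside its four listed circumstances qualifies, and the consent wording it reproduces also speaks of imminent danger.
- **Depression / PHQ-9 (Sources of Materials).** Item 9 asks about "Thoughts that you would be better off dead or of hurting yourself". For any answer other than none, "at any of the scheduled visits (baseline, 12 or 24-weeks), the project manager will contact the lead PI" and the contact PI for guidance. Law enforcement is called only at imminent risk, and the reader is sent to the Data and Safety Monitoring Plan for details.
- **Reporting to NINR.** Serious adverse events go to NINR within 72 hours; other adverse events go in at least yearly, with the progress report.

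**The concern.** Suicidal thoughts are a foreseeable event here. They are screened for at baseline, 12 and 24 weeks in a population the plan itself calls vulnerable, and coaches raise stigma and distress in the sessions. Two staff members who each follow the text in good faith could handle the same non-imminent disclosure differently. One would log an adverse event for the annual report and keep confidentiality. The other would start an emergency referral, treat the event as serious, and disclose.

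Three things are at stake: the participant's safety and privacy, the truth of what participants are told about privacy when they consent, and whether the funder hears of an event in three days or at the next annual report.

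**Working it through.** No arithmetic applies, and the plan gives no figure to reproduce. The check is to put one case through each text: a participant reports suicidal ideation and is judged not to be in imminent danger.

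**Step 1: seriousness.**

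| Text | Test applied | Class of this case | Report to NINR |
|---|---|---|---|
| Adverse Events, definition | Imminent danger | Adverse event | At least yearly |
| Adverse Events, coach training | Ideation | Serious adverse event | Within 72 hours |
| Reporting Adverse Events | Ideation | Serious adverse event, with immediate psychiatric emergency referral | Within 72 hours |

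The class in the first row follows from applying the definition. No passage labels ideation a plain adverse event in so many words.

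**Step 2: can the reporting text be read as meaning imminent ideation only?** Its own structure is against this. After the referral and crisis-line steps it gives the imminent life-threatening emergency its own step, 911. If ideation as a serious event already meant imminent danger, that separate step would add little. The coach-training text carries no qualifier either.

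**Step 3: does the later decision on seriousness resolve it?** The Vice Dean and IRB Chairperson decide whether an event is serious, but they are given both rules. Under one, this case is already serious by name; under the other, it cannot be. The emergency referral is also tied to the staff-level label and is not made to wait for their decision.

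**Step 4: confidentiality.**

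| Text | Condition for breaking confidentiality | This case |
|---|---|---|
| Exceptions to Confidentiality | "if a participant reports current suicidality and is in imminent danger of suicide" | Kept |
| Consent wording reproduced in that section | Imminent danger | Kept |
| Reporting Adverse Events | Current suicidality alone | Broken, if ideation counts as current suicidality |

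Because the first text closes its list, the third cannot be read as an addition to it. Because the third cites the consent form, the plan also gives two accounts of what participants are told.

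**Step 5: the PHQ-9 route.** Item 9 covers passive thoughts as well as thoughts of self-harm and does not grade imminence. The response, "the project manager will contact the lead PI" and the contact PI, assigns no class. The section then refers to the monitoring plan, which is where the conflict in steps 1 and 4 sits. No passage says whether a positive answer counts as ideation or as current suicidality.

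**The case against.** The best defence is that the plan is graded: guidance first, emergency measures only when risk is imminent, and seriousness settled by senior officials. Much of this is fair. The PHQ-9 section and the Exceptions to Confidentiality section both work that way. The reporting text does use imminence in places, including the 911 step. SAE status does not follow automatically from one staff member's reading. The defence fails only on the two clauses without the qualifier: ideation named as a serious adverse event (twice), and the confidentiality sentence.

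Several stronger readings are tempting, but the documents do not support them.

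- **That suicidality is handled in three incompatible ways.** There are two regimes. The call for guidance after item 9 is a first contact, not a class, and fits either.
- **That every positive item 9 answer is a serious adverse event, so SAEs can be counted.** Item 9 could be asked up to 120 × 3 = 360 times, but the documents give no rate of positive answers and no mapping from an answer to ideation. Seriousness is also decided case by case. The 360 is a number of askings, not of events.
- **That the 24-hour IRB report depends on which text is followed.** The Reporting to NYU IRB section puts serious and certain non-serious events on the same clock. In both cases the event must be unexpected and at least possibly related. Seriousness matters only because non-serious events must also suggest greater risk than was known.
- **That safety data would not be comparable between arms.** Item 9 is asked at the same visits in both arms, and the documents show no mechanism for a difference.
- **That remote participants have no pathway.** They do: investigators call 911 and join by Zoom. The sentence about imminent risk "during in-person interview (focus group or post intervention interview" sits oddly beside assessments done by videoconference, but it is at most an editorial matter.

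The consent pages are not in the reviewed text, so what participants actually read cannot be checked.

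**Conclusion.** The point holds as two direct contradictions in the plan's own rules. First, ideation without imminent danger is an adverse event under the stated definition and a serious adverse event under the training and reporting text. This changes the emergency referral and moves the NINR report from annual to 72 hours. Second, confidentiality may be broken only with imminent danger in one section and must be broken for current suicidality alone in another. The silence on how item 9 answers are classed leaves the screening route exposed to both.

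The size is qualitative, and no number of affected participants can be given. The conclusion rests on reading ideation in the reporting text as not limited to imminent danger, which its separate 911 step supports. The second contradiction also assumes that ideation counts as current suicidality. Which rule is clinically right is outside this point. These are conflicting rules, not missing detail, and they should be corrected.

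**What to change.** Reconcile the PHQ-9 text, Exceptions to Confidentiality, Adverse Events (both the definition and the coach-training text) and Reporting Adverse Events (including the joint decision on seriousness) so that together they give:

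1. one definition of a serious adverse event, applied to suicidality in the same words throughout;
2. one pathway, stating who is contacted, who assigns the class, and which steps do or do not wait for that decision;
3. one threshold for breaking confidentiality;
4. an explicit statement of how item 9 answers map to the definition and the threshold.

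Then check the consent form against the agreed threshold and correct whichever text differs. The in-person interview wording can be tidied at the same time. The clinical content is for the investigators and the IRB to set.

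The cost is a protocol amendment, a consent revision if the check shows one is needed, and retraining of the project manager and coaches. No new data or staff are required.

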## **POTENTIAL BENEFITS OF THE PROPOSED RESEARCH TO HUMAN SUBJECTS AND OTHERS**

**Potential Benefits.** Improving ART adherence and viral load suppression for Black and Hispanic HIV+AYA is an urgent public health matter. We developed ACCESS II RCT for Black and Hispanic HIV+AYA in response to critical methodological challenges with conventional approaches and persistent minority health disparities leading to poor HIV virologic control. Our approach is highly promising for HIV behavioral science, with potential broad effect on clinical treatment and prevention through the development of a scalable adherence intervention. By reducing the structural barriers of travel and stigma, technology-enabled interventions can reduce minority health disparities. Mobilizing peer health coaches using videoconferencing technology is a viable way to deliver a behavioral intervention targeting ART adherence with a stigmatized and hard to reach population. Our prior work demonstrated feasibility, acceptability, and improvement in HIV viral load and ART adherence. Furthermore,

there is a call for greater mobilization of peer health coaches to support HIV health outcomes, including adherence. ACCESS II RCT will be complimentary to current national and public health peer initiatives targeting HIV+ and at-risk AYA.

**Importance of the Knowledge to be Gained.** One million US individuals are HIV+ including 100,000 AYA, ages 15-29 years. Black and Hispanic AYA are disproportionately represented in the US HIV health crisis. Antiretroviral therapy (ART) effectively treats HIV infection and prevents HIV-related morbidity, mortality and sexual transmission, but improved health outcomes are related to behavior: benefits of ART are directly proportional to levels of adherence. Optimal adherence is defined as 80 to 90% for protease-inhibitor-boosted regimens and greater than 90% for un-boosted regimens. Black and Hispanic HIV+AYA have the lowest rates of ART adherence; nearly 40% reported suboptimal adherence (<90%) during the past week. Virologic estimates show that only half of US AYA (ages 13-24 years) achieved suppression (HIV RNA level of <200 copies/ml). Black and Hispanic HIV+ AYA are at high risk for virologic failure during their entire HIV treatment course, even after a period of virologic suppression. Persistent HIV viremia due to suboptimal ART adherence is a primary contributor to the increasing number of HIV infections. A shift in the current approach to ART adherence support is desperately needed.

#### **Reasonableness of Subjects' Risks in Relation to Anticipated Benefits.**

The human subjects' risks are related to loss of confidentiality, perceived pressure to participate, embarrassment related to suboptimal adherence, and/or difficulty using the mobile application for remote videoconferencing. Training procedures directed to peer health coaches and collaborative efforts with NYU Meyers IT will minimize these risks. Additionally, the Data and Safety Monitoring Plan is intended to address and monitor these risks and any potential threats to safety. Given the importance of the problem of suboptimal adherence in HIV+ AYA, the potential importance of the knowledge to be gained outweigh these potential risks to human subjects.

#### **INCLUSION OF WOMEN AND MINORITIES**

HIV-infection is primarily characterized as a disease mostly affecting non-whites and minorities. We expect our sample population to be largely comprised of Black and Hispanic AYA. Based on the current demographics of the clinic population across these three clinical settings, we expect less than 5.0% of the sample to be White, 60.0% - 70.0% of the population to be Black and 30.0% - 40.0% to be Hispanic. Given the current demographic characteristics of the population across the three clinical settings, we anticipate 40.0% - 45.0% of the sample to be female. These estimates are based on experience with recruitment for the completed K23 research study with HIV+ AYA.

